Exploratory objectives	Analysis of biopsy tissue for differences between pre- and post-treatment samples correlation to patient survival e.g.: 

• T cell receptor (TCR) clonality

• Tumor-Infiltrating-Lymphocytes (TILs)

• Protein expression for e.g. Programmed Death Ligand 1 (PD-L1) and other biomarkers

• Gene expression profiling for molecular subtyping

 Analysis of tumor DNA for Tumor mutational burden; DNA damage response gene mutations, MSI status, MMR deficiency status  Analysis of peripheral blood mononuclear cells (PBMCs) / serum for differences between pre- and post-treatment samples correlation to patient survival e.g.: 

• Antigen-specific immune responses to carcinoembryonic antigen (CEA) and mucin-1 (MUC-1) as well as to other tumor-associated antigens (TAAs) to assess antigen cascade

• Immunophenotyping of immune cell subsets by flow cytometry

• Soluble biomarkers (e.g. cytokines and classical tumor markers)

• TCR clonality

• PD-1/L1 staining

Primary endpoint	Proportion of subjects with a confirmed OR (CR+PR) as per investigator assessment according to RECIST 1.1.

---

Secondary endpoints	
Safety of the combined treatment as measured by:
 

• Adverse Events (incidence, severity, and seriousness of treatment emergent adverse events [TEAEs])

• Laboratory Measures (summaries and shifts from baseline)

• Vital Signs (summaries)

 
OS defined as the time from start of treatment to the time of death from any cause.
 
Duration of response defined as the time from the initial occurrence of documented complete response (CR) or partial response (PR) (whichever occurred first) until documented disease progression or death due to any cause on trial, whichever occurred first.
 
PFS defined as the time from start of treatment to the first event of death or progressive disease (PD) per RECIST 1.1.
 
Percentage of participants with OS and PFS at 6 (PFS only), 9 (PFS only), 12, 18 and 24 months.
 
Immune-related Response Criteria assessment of response rate per iRECIST, delayed responses (pseudo-progressions), duration of response and PFS.

Trial design	Phase 2, Multicenter, Single-Arm, 2 Cohorts, Two-stage

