## **9.7 Efficacy Analysis**

### **9.7.1 Primary Efficacy Analysis**

The ORR is defined as the proportion of subjects with an objective tumor response (CR or PR) based on RECIST 1.1 evaluations as performed by the investigator. Based on prior published results with atezolizumab, the null ORR for Cohort 1 is 0.23, and for Cohort 2 is 0.15.

Cohort 1: In the first stage, 14 subjects will be accrued. If there are 3 or fewer responses in these 14 subjects, the cohort will be stopped. Otherwise, 19 additional subjects will be accrued for a total of 33. The null hypothesis will be rejected if 13 or more responses are observed in 33 subjects. This design yields an actual type I error rate of 0.0244 and power of 0.7027 when the true ORR is 0.43 for the combination.

Cohort 2: In the first stage, 13 subjects will be accrued. If there are 2 or fewer responses in these 13 subjects, the cohort will be stopped. Otherwise, 22 additional subjects will be accrued for a total of 35. The null hypothesis will be rejected if 10 or more responses are observed in 35 subjects. This design yields an actual type I error rate of 0.0249 and power of 0.7092 when the true ORR is 0.33 for the combination.

In the case that the number of responses required to move to Stage 2, individually per cohort, is met in the FAS population, the study will move to Stage 2 without enrolling the full EE Set. If Stage 1 results are not clear after enrolling the prescribed number of Stage 1 subjects in the FAS, enrollment will continue until the EE Set meets the prescribed number of Stage 1 subjects for the interim futility analysis. In the event continuing enrollment of the EE Set would still not produce a positive outcome for Stage 1, the cohort will be discontinued without meeting the full Stage 1 sample size for the EE set.

For the final primary efficacy analysis, the number and percent of subjects with OR, and in each category of objective tumor response, will be summarized based on the FAS. The two-sided 90% exact binomial confidence interval for the ORR will be calculated using the Clopper-Pearson method.

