### 17.3 Appendix 3: Algorithm for Reporting of AESIs

## 17.4 Appendix 4: RECIST 1.1 Criteria

The best overall response is the best response recorded from the start of treatment until disease progression/recurrence, taking as reference for progressive disease the smallest measurements recorded since treatment started. The patient's best response assignment will depend on the achievement of both measurement and confirmation criteria.

Target Lesions	Non-target Lesions	New Lesions*	Overall Response	Best Overall Response when confirmation is required
CR	CR	No	CR	> 4 week confirmation**
CR	Non-CR/non-PD	No	PR	> 4 week confirmation**
CR	Not evaluated	No	PR	> 4 week confirmation**
PR	Non-CR/non-PD/not evaluated	No	PR	> 4 week confirmation**
SD	Non-CR/non-PD/not evaluated	No	SD	Documented at least once 4 weeks from baseline**
PD	Any	Yes or no	PD	No prior SD, PR, or CR
Any	PD***	Yes or no	PD	No prior SD, PR, or CR
Any	Any	Yes	PD	No prior SD, PR, or CR

\*See RECIST 1.1 Manuscript for further details on what is evidence of new lesions.

\*\*Only for non-randomized trials with response as primary endpoint

\*\*\*In exceptional circumstances, unequivocal progression in non-target lesions may be accepted as disease progression.

Confirmation: To be assigned a status of PR or CR, changes in tumor measurements must be confirmed by repeat assessments that should be performed at least 4 weeks after the criteria for response are first met.

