2.6 Endpoints

2.6.1 Primary Endpoint

ORR, defined as the proportion of subjects with a confirmed objective response (CR+PR) per investigator assessment according to RECIST v1.1.

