2.6.4.1 Primary Interim Analysis

The first post-treatment objective radiographic response assessment by the investigator will occur approximately 10 weeks after first treatment, with the second occurring 12 weeks later at the Week 22 visit. When the first 14 subjects in the FAS in Cohort 1, or the first 13 subjects in the FAS in Cohort 2 have completed at least 2 post-baseline CT scans (or MRIs if applicable), analysis for the FAS will be performed. If the number of responders meets the Stage 1 continuation criterion (> 3 responses for Cohort 1 or > 2 responses for Cohort 2), enrollment for the cohort will continue until the FAS has a total 33 subjects in Cohort 1, or 35 subjects in Cohort 2. Subjects who are enrolled to the EE set for the Stage 1 sensitivity analyses will be included as part of the total number of subjects in the FAS.

For subjects who have completed multiple scans, the best objective response will be used. Since the number of responders is continuously monitored, if the continuation criterion is met in either cohort in the FAS before the first 14 subjects in Cohort 1 and the first 13

subjects in Cohort 2 have completed at least 2 post-baseline tumor assessments, enrollment for the cohort will resume as described above.

If the number of responders does not meet the continuation criterion when the first 14 subjects in the FAS in Cohort 1, or the first 13 subjects in the FAS in Cohort 2, have completed at least 2 post-baseline tumor assessments, progress prior to having 2 post-baseline tumor assessments, or discontinue early from the trial, the combination treatment for the cohort will not be considered promising.

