4.4.5 Efficacy Analyses

4.4.5.1 Primary Endpoint

The primary efficacy endpoint for the trial is the ORR, defined as the proportion of subjects achieving CR or PR, whichever occurs first, based on investigator-assessed RECIST v1.1 evaluations. Due to the Simon's 2-stage design, hypothesis testing will occur at the end of Stage 1 (interim analysis), and if successful, at the end of Stage 2 within each cohort.

The success criteria are based on the point estimate of the FAS within each cohort. For Cohort 1, at least 4 responses are required in the first 14 subjects to move to Stage 2. For the final Cohort 1 analysis, the null hypothesis that ORR is no more than 0.23 will be rejected if 13 or more responses are observed in the 33 subjects of the FAS. For Cohort 2, at least 3 responses are required in the first 13 subjects to move to Stage 2. For the final Cohort 2 analysis, the null hypothesis that the ORR is no more than 0.15 will be rejected if 10 or more responses are observed in the 35 subjects of the FAS.

In case the number of subjects in the analysis set(s) exceeds the planned sample size, the success criteria will be chosen to preserve the design type I error rate of 0.025 (one-sided) using the exact 2-stage binomial calculation (replacing p with p_0 in formula [1], [Section 2.6.4.2](#)). Type I error equals 1 minus the result from formula [1] when $p = p_0$.

For the final trial analysis, the number and percentage of subjects in each RECIST v1.1 response category, as well as those with a best objective response of CR or PR, will be summarized based on the FAS. The two-sided 90% exact binomial confidence interval for the ORR will be calculated using the Clopper-Pearson method.

Sensitivity analyses will be explored at the end of the trial based on a repeated analysis for any potential immune-related responses observed, as well as a repeat of the analysis on the EE set. For immune-related response cases, ORR analyses using iRECIST criteria will also be provided. For iRECIST, complete or partial responses are still able to be achieved after an initial unconfirmed progression, whereas with RECIST v1.1 once any evidence of progression is recorded, no further responses can be evaluated. For subjects who are not evaluated by iRECIST criteria, their tumor response based on RECIST v1.1 response guidelines will be used.

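### The plan does not settle whether Stage 1 and the final ORR test count confirmed or unconfirmed responses; if confirmed, the two-scan trigger can decide futility before a Week 22 response has been confirmed

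*SAP*

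**What the plan says.** **Endpoint.** The Protocol synopsis (1.4) gives the primary endpoint as "Proportion of subjects with a confirmed OR (CR+PR) as per investigator assessment according to RECIST 1.1". SAP 2.6.1 agrees: "defined as the proportion of subjects with a confirmed objective response (CR+PR) per investigator assessment". Protocol Appendix 4 (17.4) says that changes in tumor measurement "must be confirmed by repeat assessments that should be performed at least 4 weeks after the criteria for response are first met", and adds: "The patient's best response assignment will depend on the achievement of both measurement and confirmation criteria".

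**Analysis.** Protocol 9.7.1 reads "The ORR is defined as the proportion of subjects with an objective tumor response (CR or PR) based on RECIST 1.1 evaluations". SAP 4.4.5.1 has ORR "defined as the proportion of subjects achieving CR or PR, whichever occurs first, based on investigator-assessed RECIST v1.1 evaluations". The primary objective in SAP 2.3.1 likewise speaks of a best response of CR or PR. None of the three mentions confirmation.

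**Stage 1.** SAP 2.6.4.1 places the first two post-treatment scans at about Week 10 and at Week 22. Once the first 14 (Cohort 1) or 13 (Cohort 2) subjects of the full analysis set (FAS) "have completed at least 2 post-baseline CT scans (or MRIs if applicable), analysis for the FAS will be performed". Each subject's best objective response is used. A cohort with fewer than 4 (3) responders at that point is judged not promising. SAP 2.6.4.2 offers a further route through the efficacy evaluable (EE) set, triggered by the same two scans. The next scheduled scan after Week 22 is at Week 28 (Protocol 1.5).

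**The concern.** The Stage 1 rule can end a cohort, so what it counts has to be fixed in advance. The text allows two readings, and they err in opposite directions.

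1. **Confirmed responses count**, as the endpoint and Appendix 4 direct. A response first seen at Week 10 can be confirmed at Week 22. A response first seen at Week 22 cannot be confirmed until after the second scan, and nothing holds the decision for it. The gate is then stricter than the design assumed, and an active cohort may be stopped.
2. **Unconfirmed responses count**, as Protocol 9.7.1 and SAP 4.4.5.1 read on their face. The gate and the final test then include responses that the declared endpoint excludes.

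The trial is open-label, response is investigator-assessed, and SAP 2.6.4 has responders monitored continuously. The choice between readings could therefore be made with the responses already known.

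**Working it through.** **Inputs** (Protocol 1.4, SAP 4.1). Cohort 1: stop if 3 or fewer of 14 respond, reject the null at 13 or more of 33, p0 = 0.23, p1 = 0.43. Cohort 2: stop if 2 or fewer of 13, reject at 10 or more of 35, p0 = 0.15, p1 = 0.33. Let n1 and n be the Stage 1 and total sizes, r1 the stopping bound (3; 2) and r the largest non-rejecting total (12; 9).

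**Step 1: reproduce the design.**

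P(stop) = Σ b(x; p, n1) over x ≤ r1.

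P(reject) = Σ b(x; p, n1) · P[Bin(n − n1, p) ≥ r + 1 − x] over x > r1.

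- Cohort 1: type I error 0.0244, power 0.7027, P(stop) at p1 = 0.084.
- Cohort 2: type I error 0.0249, power 0.7092, P(stop) at p1 = 0.144.

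The type I errors and powers match the stated figures to four decimals.

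**Step 2: timing.** Planned days are 64 (Week 10), 148 (Week 22) and 190 (Week 28).

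- Week 10 to Week 22: 148 − 64 = 84 days, so a Week 10 response is confirmable at the second scan.
- Week 22 to Week 28: 190 − 148 = 42 days. With the visit windows in SAP Table 1 the shortest gap is 183 − 152 = 31 days. Week 28 can therefore confirm a Week 22 response, but it falls after the trigger.

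**Step 3: first reading (confirmation applied).** Two quantities are not in the documents and are assumed:

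- k = number of Stage 1 subjects who have only two scans at the decision;
- f = share of eventual responders among those k who are still unconfirmed.

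The other n1 − k subjects contribute A ~ Bin(n1 − k, p). The k subjects contribute X ~ Bin(k, p) eventual responders, of whom Y ~ Bin(X, 1 − f) count at the decision. The cohort stops if A + Y ≤ r1. Otherwise the null is rejected if A + X + Bin(n − n1, p) ≥ r + 1. Results at p1 with f = 20%:

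| k | Cohort 1 stop | Cohort 1 power | Cohort 2 stop | Cohort 2 power |
|---|---|---|---|---|
| 0 (as designed) | 8.4% | 0.703 | 14.4% | 0.709 |
| 4 | 11.5% | 0.688 | 18.2% | 0.685 |
| 7 | 14.5% | 0.673 | 21.4% | 0.663 |
| all (14; 13) | 23.5% | 0.617 | 29.2% | 0.606 |

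The last row can be checked directly. In Cohort 1 the rate counted at the decision is 0.43 × 0.8 = 0.344, and P[Bin(14, 0.344) ≤ 3] = 0.235. In Cohort 2 it is 0.33 × 0.8 = 0.264, and P[Bin(13, 0.264) ≤ 2] = 0.292.

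Power for at least one positive cohort is 1 − (1 − 0.703)(1 − 0.709) = 0.914 as designed, and 1 − (1 − 0.617)(1 − 0.606) = 0.849 in the last row.

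**Step 4: second reading (confirmation not applied).** Suppose a share u of counted responses would fail to confirm and the null rates are confirmed rates. The counted rate under the null is then p0/(1 − u), put into the Step 1 formula:

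- u = 5%: Cohort 1, 0.23/0.95 = 0.242, type I error 0.036; Cohort 2, 0.15/0.95 = 0.158, type I error 0.034.
- u = 15%: Cohort 1, 0.23/0.85 = 0.271, type I error 0.080; Cohort 2, 0.15/0.85 = 0.176, type I error 0.066.

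**The case against.** **The stronger reading is not written down.** A reader might infer that the SAP scores a response first seen at Week 22 as no response. It does not say so. SAP 2.6.4.1 is silent on confirmation, and the non-responder rule in SAP 4.3.3 covers subjects with no CR or PR on record who withdraw or are lost. This objection stands: the false stop follows only if confirmation is enforced at the interim.

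**The two harms do not add up.** A reader might infer that the plan both loses power and inflates type I error. Each belongs to a reading that rules out the other. This stands too.

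**Not every Stage 1 subject is affected.** The trigger is at least two scans in all 14 (13) subjects, so earlier enrollees may already have had Week 28. The bottom row of the table is therefore an upper bound for the assumed f. In addition, first responses after Week 22 are invisible at a two-scan decision whether or not confirmation is required, so they should not be included in f.

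**Confirmation is not lost from the protocol.** Appendix 4 makes best response depend on it, and the analysis sections can be read as shorthand. That favors the first reading, which is the one where the timing problem arises. It does not remove the need to align the text.

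**The null rates may not be confirmed rates.** The documents do not say whether the 23% and 15% benchmarks count only confirmed responses. If they do not, the Step 4 inflation need not arise.

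**The EE route and later updates.** The EE route adds subjects under the same two-scan trigger and does not wait for a pending confirmation. Protocol 9.12 allows updated analyses as follow-up matures, but neither document says that such an update reverses a futility stop.

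**Conclusion.** The point holds as an unresolved definition with a timing gap. The endpoint is confirmed response, three sections define the tested ORR without confirmation, and the Stage 1 rule does not say which applies.

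If confirmation is applied, a cohort can be declared not promising while a response first seen at Week 22 in a recently enrolled subject awaits Week 28. With f = 20%, the added false-stop probability at the target ORR runs from about 3 percentage points (k = 4: 11.5 − 8.4 = 3.1) to at most 15 (23.5 − 8.4 = 15.1) in Cohort 1, and from about 4 (18.2 − 14.4 = 3.8) to at most 15 (29.2 − 14.4 = 14.8) in Cohort 2. Both f and k are assumptions.

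If confirmation is not applied, type I error of 0.036 to 0.080 (Cohort 1) and 0.034 to 0.066 (Cohort 2) follows only if 5% to 15% of counted responses fail to confirm and the benchmarks are confirmed rates. The documents state neither, so this range is illustrative.

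**What to change.** 1. Write confirmed response into Protocol 9.7.1 and SAP 2.3.1, 2.6.4.1 and 4.4.5.1, to match the synopsis, SAP 2.6.1 and Appendix 4.
2. Add to SAP 2.6.4.1 and 2.6.4.2: a cohort with fewer than 4 (Cohort 1) or 3 (Cohort 2) confirmed responses is not declared futile while any unconfirmed CR or PR that could change the decision awaits its next scheduled scan.
3. Apply the same rule at the final cut-off.

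The cost is an amendment to the wording of both documents and a Stage 1 decision that may come about 6 weeks later (Week 22 to Week 28). The wait applies only when a pending response could change the outcome, and only scheduled scans are used. With no response pending at the decision, the stated type I error and power apply unchanged.

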2.6.4.2 Sensitivity Interim Analysis

If the success criterion can be met in the EE set, the cohort will continue until the number of subjects in the EE set reaches the Stage 1 sample size, and a sensitivity analysis will be performed when all subjects in the EE set have completed at least 2 post-baseline tumor assessments, progress prior to having 2 post-baseline tumor assessments, or discontinue early from the trial.

- If the number of responders in the EE set does not meet the Stage 1 continuation criterion, the cohort will be discontinued. If the number of subjects completing 2 post-baseline tumor assessment in the EE set exceeds the planned Stage 1 sample size at time of the interim analysis, the Stage 1 stopping rule will be based on a revised criterion ε_1 , where ε_1 is the largest integer for which the power would remain above 70% for each cohort by assuming the planned n is the final total number of EE subjects. The probability of rejecting the treatment is

$$B(\varepsilon_1; p, m_1) + \sum_{x=\varepsilon_1+1}^{\min(m_1, r)} b(x; p, m_1) B(r - x; p, n - m_1), \quad [1]$$

where $B(\varepsilon_1; p, m_1)$ and $b(x; p, m_1)$ are the binomial distribution and density function; m_1 is the Stage 1 sample size, and r is the design rejection criterion at the end of the trial when the sample size is n (Simon, 1989). When p equals the alternative hypothesis, [1] represents the type II error, β , and thus the power equals $1 - \beta$.

- If the number of responders in the EE set meets the Stage 1 continuation criterion ($>\varepsilon_1$), a further decision will be made whether to continue to Stage 2 to enroll a total of 33 evaluable subjects in Cohort 1 or 35 evaluable subjects in Cohort 2 for sensitivity analyses. If a strong signal in the EE set is not observed, the cohort will be discontinued. If there is a high probability ($>50\%$) that the alternative hypothesis (43% in Cohort 1 and 33% in Cohort 2) is true based on data obtained from Stage 1, the cohort will continue to Stage 2 based on the EE set. The posterior probability will be calculated based on a non-informative prior, $p \sim \text{Beta}(1,1)$.

3 Trial Design

Trial Procedure	Screening Phase Day -28 to Day 1	Week (3 wk interval +/- 4 days)						Week (6 wk interval +/- 1 wk)		Week (12 wk interval +/- 2 wks)						Long Term FU													
		1	4	7	10	13	16	22	28	40	52	64	76	88	100 EOT ¹²	3-month interval +/- 2 wks													
		Day																											
		1	22	43	64	85	106	148	190	274	358	442	526	610	694 EOT														
Visit																													
1																	2	3	4	5	6	7	8	9	10	11	12	13	14
Trial Procedures																													
Informed Consent ¹	X																												
Demographics	X																												
Medical History	X																												
Physical Exam incl. vital signs ²	X																												
Targeted PE incl. vital signs ²		X	X	X	X	X	X	X	X	X	X	X	X	X	X	X													
ECOG	X	X	X	X	X	X	X	X	X	X	X	X	X	X	X	X													
ECG ³	X																												
Eligibility Criteria	X																												
Concomitant Medications	X	collected at all clinic visits (including atezolizumab dosing visits)																											
Adverse Events ⁴	X	collected at all clinic visits (including atezolizumab dosing visits)														X ⁴													
Survival Status and Auto-immune/ IM clinical manifestation																X													
Tumor Biopsy	X ⁵			X ⁶																									
Radiology Assessments																													
CT scan: Thorax, Abdomen and Pelvis ⁷	X			X				X	X	X	X	X	X	X	X	X													

Trial Procedure	Screening Phase Day -28 to Day 1	Week (3 wk interval +/- 4 days)						Week (6 wk interval +/- 1 wk)		Week (12 wk interval +/- 2 wks)						Long Term FU	
		1	4	7	10	13	16	22	28	40	52	64	76	88	100 EOT ¹²	3-month interval +/- 2 wks	
		Day															
		1	22	43	64	85	106	148	190	274	358	442	526	610	694 EOT		
		Visit															
		1	2	3	4	5	6	7	8	9	10	11	12	13	14		
Laboratory Assessments																	
Hematology ⁸	X	X	X	X	X	X	X	X	X	X	X	X	X	X	X	X	
Serum Chemistry ⁸	X	X	X	X	X	X	X	X	X	X	X	X	X	X	X	X	
HIV, HbsAg, HCV	X																
INR, PT, aPTT	X																
Thyroid function test	X	X		X		X											
Biomarker Analyses ⁹	X		X		X			X			X						
Urinalysis	X		X		X		X	X	X	X	X	X	X	X	X	X	
Pregnancy Test ¹⁰	X	X	X	X	X	X	X	X	X	X	X	X	X	X	X	X	
Dosing																	
Prime Vaccine: MVA-BN-CV301 ¹¹		X	X														
Boost Vaccine: FPV-CV301 ¹¹				X	X	X	X	X	X	X	X	X	X	X	X	X	
Atezolizumab		X	X	X	X	X	X										

EOT = End of Treatment, PE = Physical Examination, AE = Adverse Event, SAE = Serious Adverse Event, AESI = Adverse Event of Special Interest, WOCBP = Women of Childbearing Potential

¹ ICF can be obtained prior to Screening visit

² Blood pressure and pulse rate should be obtained after the subject has been seated in an upright position for at least 5 minutes.

³ Troponin I will only be measured if clinically indicated.

⁴ The reporting period for non-serious AEs and unrelated SAEs/AESIs ends 30 days after last administration of the trial product. The reporting period for related SAEs/AESIs ends 100 days after last administration of the trial product. A phone follow-up will be performed 100 days after the last administration of trial product to collect this information and schedule a follow-up visit, if clinically indicated.

⁵ Patients who do not have archived tissue specimens meeting eligibility requirements must undergo a biopsy sample collection during the screening period. Acceptable samples included core needle biopsies for deep tumor tissue (minimum three cores) or excisional, incisional, punch, or forceps biopsy samples for cutaneous, subcutaneous, or mucosal lesions.

⁶ Optional at any of the following visits: Visit 3-6.

⁷ If there is a medical reason, subject may have MRI instead of CT scan upon approval from BN.

⁸ Hematology and Serum Chemistry will be performed prior to every atezolizumab infusion. Hematology will include hemoglobin, hematocrit, red blood cell count, total white blood cell count with differential, platelet count, mean cell volume, mean corpuscular hemoglobin, and red blood cell distribution width. Serum chemistry will include: total protein, albumin, alkaline phosphatase, total bilirubin, ALT, AST, lactate dehydrogenase, creatinine, blood urea nitrogen, uric acid, glucose, calcium, phosphorus, bicarbonate, chloride, potassium, sodium, lipase and amylase.

⁹ Sample collection (peripheral blood for PBMC, serum) must occur prior to vaccine dosing. Sample collection for Biomarker analyses should be repeated if subject comes off trial due to PD or AE or if the subject has an objective response.

¹⁰ For WOCBP, a pregnancy test is required prior to every atezolizumab infusion. Urine or serum pregnancy test is acceptable at any given visit depending on investigator and/or patient preference.

¹¹ The trial subject must be kept under close observation at the clinical trial site for at least 30 minutes following vaccinations.

¹² EOT visit should take place within 28 days of withdrawal.

4 Statistical Methods

